9.7.2.3 Descriptive Analysis

[figure not shown]
9.7.2.3.1 Description of Study Enrollment

The study populations as identified in the recruitment process will be described. Recruitment rates and a description of the number of patients/caregivers in the study and analysis populations will be provided.

Analysis sets: As shown in [Figure 3](#), datasets for analysis will be further described in the SAP and will include:

- Study population: All adult patients with R/R Ph- B-precursor ALL initiating Blincyto (or their caregivers).
- Eligible Set: All patients/caregivers who fulfill the eligibility criteria.
- Enrolled Set: All eligible patients/caregivers who agree to participate in the study.
- Full Analysis Set: All patients/caregivers who complete the questionnaire of their corresponding survey and have valid responses to allow for the assessment of the primary objective.
- Safety Set: This is the same as the Enrolled Set.

Figure 3. Study Population and Datasets flow-chart

9.7.2.3.2 Description of Subject/Patient Characteristics

The following sociodemographic and treatment characteristics will be summarised: age group, gender, country, respondent type, educational level and **time since Blincyto initiation**.

9.7.2.4 Analysis of the Primary and Secondary Endpoint(s)

The primary analysis for the survey will be performed for patients and caregivers separately for the endpoints below described, and will include the total number of patients and caregivers with valid responses to all relevant questions and the percentage of patients and caregivers with a positive response for the endpoint:

- **Receipt** will be assessed through the percentage of patients and caregivers who received the brochure and/or card.
- A mean **knowledge** score will be created to summarise individual patient and caregiver scores. An individual patient/caregiver score is calculated as the proportion of all knowledge questions with correct responses.

The secondary analyses are:

- A mean **behaviour** score will be created to summarise individual patient and caregiver scores. An individual patient/caregiver score is calculated as the proportion of all behaviour questions with correct responses.
- Among patient and caregivers who have read the patient/caregiver brochure and/or card, an ordinal scale will describe the self-reported level of **understanding**.
- A mean **usage** score will be created to summarise individual patient and caregiver scores. An individual patient/caregiver score is calculated as the sum of the 'value' of responses to all usage questions (ordinal scale) divided by the maximum possible

score. Among patients and caregivers who have not read the materials, a categorical variable will describe the reasons for not reading them.

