The study population will include approximately [CCI] patients and/or their associated caregivers to allow precisions of – [CCI] for correct responses of 60 and 90%, respectively, for the primary endpoint of receipt. For the score of correct responses to knowledge questions ranging from 0 to 10, when the estimated standard deviation ranges from [CCI], a sample size of [CCI] patients and [CCI] caregivers will produce a two-sided 95% confidence interval with a distance from the mean to the limits ranging from [CCI]

- **Data Analysis**

Categorical data will be summarized by counts and percentages. Continuous data will be summarized using number, mean, standard deviation (SD), median, quartiles, minimum and maximum and in the case of non-normally distributed data, median, range and interquartile range. 95% confidence intervals will be presented to three decimal places.

Analyses will be mainly descriptive for the overall study population and certain subgroups, such as those who read the material vs. those who did not. The statistical analysis will include a summary of the study conduct, a descriptive analysis and the analysis of the objectives.

Receipt will be described through the percentage of patients and caregivers who report having received the patient/caregiver card and/or brochure.

Knowledge: A mean score will be created to summarise individual patient and caregiver scores. An individual patient/caregiver score is calculated as the proportion of all knowledge questions with correct responses.

Behaviour: A mean score will be created to summarise individual patient and caregiver scores. An individual patient/caregiver score is calculated as the proportion of all behaviour questions with correct responses.

Understanding: Among patients and caregivers who have read the patient/caregiver brochure and/or card, an ordinal scale will describe the self-reported level of understanding.

Usage: A mean score will be created to summarise individual patient and caregiver scores. An individual patient/caregiver score will be calculated as the sum of the 'value' of responses to all usage questions (ordinal scale) divided by the maximum possible score. Among patient and caregivers who have not read the materials, a categorical variable will describe the reasons for not reading them.

5. Amendments and Updates

Amendment or Update No.	Date	Section of Study Protocol	Amendment or Update	Reason
1	06 November 2017	See Summary of Changes		

6. Milestones

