8.2 Secondary

The secondary objectives of the study are:

- To describe behaviours outlined in the patient/caregiver educational materials, among patients with Ph– R/R B-precursor ALL receiving Blincyto and their caregivers.
- To describe the level of understanding of key safety messages in the patient/caregiver educational materials, among patients with Ph– R/R B-precursor ALL receiving Blincyto and their caregivers.
- To describe usage of the educational materials, among patients with Ph– R/R B-precursor ALL receiving Blincyto and their caregivers.

This study will help indicate if the aRMMs are successful if a majority of patients and caregivers participating in the survey confirm receipt of the patient/caregiver brochure and card and have knowledge of key safety messages in the patient/caregiver brochure. These results will be interpreted in context of the wider study including the secondary objectives and the results of individual questions, response rate and recruitment. In addition, any available information external to the study to help understand the experience of the patient aRMMs will be considered to determine what action, if any, should be taken.

9. Research Methods

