9.3.2 Outcome Assessment

The primary endpoints for the patient/caregiver survey are:

- Receipt: A categorical variable will describe if patients and caregivers received the brochure and/or card.
- Knowledge: A mean score will be created to summarise individual patient and caregiver scores. An individual patient/caregiver score is calculated as the proportion of all knowledge questions with correct responses.

The secondary endpoints for the patient/caregiver survey are:

- Behaviour: A mean score will be created to summarise individual patient and caregiver scores. An individual patient/caregiver score is calculated as the proportion of all behaviour questions with correct responses.

- **Understanding:** Among patient and caregivers who have read the patient/caregiver brochure and card, an ordinal scale will describe the self-reported level of understanding.
- **Usage:** A mean score will be created to summarise individual patient and caregiver scores. An individual patient/caregiver score is calculated as the sum of the 'value' of responses to all usage questions (ordinal scale) divided by the maximum possible score. Among patients and caregivers who have not read the materials, a categorical variable will describe the reasons for not reading them.

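### The primary receipt percentage counts brochure and/or card, while the protocol's success benchmark asks for brochure and card, so the planned figure is only an upper bound on what the benchmark needs

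*Protocol*

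**What the plan says.** Receipt is one of two primary endpoints; knowledge is the other. It is worded as a union wherever it is defined:

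- Section 4 (Abstract, Data Analysis): the "percentage of patients and caregivers who report having received the patient/caregiver card and/or brochure".
- Section 9.3.2: "A categorical variable will describe if patients and caregivers received the brochure and/or card". The categories are not listed.
- Section 9.7.2.4: receipt "will be assessed through the percentage of patients and caregivers who received the brochure and/or card".

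The benchmark for reading the result stands in section 4 and again at the end of section 8.2: "This study will help indicate if the aRMMs are successful if a majority of patients and caregivers participating in the survey" then "confirm receipt of the patient/caregiver brochure and card and have knowledge of key safety messages in the patient/caregiver brochure". Both places add that the results will be read together with the secondary objectives, individual questions, response rate, recruitment and outside information. Section 7.3 says that no formal hypothesis is tested.

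The same change of conjunction appears in the understanding endpoint. Section 9.3.2 restricts it to those "who have read the patient/caregiver brochure and card, an ordinal scale will describe" their level of understanding. Section 9.7.2.4 restricts it to those "who have read the patient/caregiver brochure and/or card, an ordinal scale will describe" it, and section 4 agrees with section 9.7.2.4.

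**The concern.** A respondent with only the card, or only the brochure, counts as positive on the primary receipt percentage but does not meet the benchmark as written.

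Table 1 shows that the two items are not interchangeable. How to avoid medication errors with the pump, the signs of neurological events and the advice not to drive are listed under the brochure. The warning to treating professionals, the prescriber's contact details and the treatment start date are listed under the card. Only the reminder to report adverse reactions is common to both. Medication errors and neurological events are the two risks for which the additional measures were required (section 7.1).

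At stake is the headline result of a study whose final report goes to the regulator's committee (section 13). The reported percentage would be set beside a benchmark that it does not measure, and any difference runs in the favourable direction. For understanding, two sections define different denominators for one endpoint.

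**Working it through.** The protocol gives no figure to reproduce. The sample size and the confidence limits in Table 2 are redacted, and no item-level receipt rate is stated. The check therefore compares the two definitions and then illustrates the gap.

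**Definitions.** Put each respondent in one of four groups, with proportions *b* (brochure only), *c* (card only), *d* (both) and *n* (neither), where *b* + *c* + *d* + *n* = 1.

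- Planned primary percentage (sections 4 and 9.7.2.4): either = *b* + *c* + *d*.
- Benchmark quantity (sections 4 and 8.2): both = *d*.
- Difference: either − both = *b* + *c*, the share holding exactly one item. It is never negative.

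So the planned figure is an upper bound on receipt of both. Taking a majority as more than 50% (an assumption, since no percentage is given), a planned figure at or below 50% would rule the benchmark out. A planned figure above 50% leaves it open.

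**Range at the protocol's own planning values.** Section 9.5 plans precision for receipt of 60% and 90%. These refer to the receipt question, not to either item. Without item-level rates, both can lie anywhere from 0 to the value of either: 0–60% when either is 60%, and 0–90% when either is 90%.

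**Illustration with assumed item rates.** Write B and C for total receipt of brochure and card. Then either = B + C − both, and both lies between max(0, B + C − 1) and min(B, C). With B = C = 60%:

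| Overlap between the items | Both | Either = 120% − both | Gap |
|---|---|---|---|
| Complete (always given together) | 60% | 60% | 0 |
| Independent | 0.6 × 0.6 = 36% | 84% | 48 points |
| Least possible | 60% + 60% − 100% = 20% | 100% | 80 points |

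In this illustration, receipt of both exceeds 50% only if more than 0.50/0.60 = 83% of those with one item also have the other. The planned percentage is above 50% in every row.

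**Another reading of the benchmark.** The sentence could mean a majority for each item separately. The planned percentage does not answer that either: 45% with the brochure only and 45% with the card only gives 45% + 45% = 90% on the planned figure, with neither item reaching a majority.

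**Understanding.** The same algebra applies to reading. The section 9.3.2 denominator (read both) is contained in the section 9.7.2.4 denominator (read at least one). They coincide only if nobody read just one item.

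**The case against.** The strongest reply has four parts.

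1. *There is no decision rule to fail.* The study is descriptive, the benchmark only helps to indicate success, and it is to be read with much else. This stands. The benchmark is interpretive, and talk of passing or failing overstates its role. It is still the only benchmark given for receipt, and the primary percentage does not measure it.

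2. *The information is probably there.* A reader might infer that the survey cannot answer its own success question. The protocol does not support that. Section 9.3.2 calls receipt a categorical variable, and section 9.9 confines the inability to separate card from brochure to some secondary-endpoint questions, with understanding and usage as examples. Receipt is not named there, so capture by item is likely, although the questionnaire is a separate document and not shown. What remains is that sections 4 and 9.7.2.4 commit the primary result to the union percentage.

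3. *Knowledge acts as a check.* A reader might infer that handing out cards alone would make the programme look successful. That goes too far, because the benchmark also requires knowledge of the brochure's messages and knowledge is itself a primary endpoint. The check is partial: Table 1 gives nurses the no-driving and symptom advice too, so patients may know it without having had the brochure.

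4. *The gap may be nil.* Both tools are owed to the same people under one obligation (section 7.1), so they may usually be given together. This also stands, and it is why the figures above are a range that includes zero. The protocol does not establish joint distribution, and the survey is there to find out what was received.

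**Conclusion.** The mismatch is real and sits in the protocol's own text. The primary receipt percentage is a union, the success benchmark is an intersection, and nothing links them. By definition the planned figure is an upper bound on receipt of both, so a majority on it does not show that the benchmark is met.

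The size is unknown. With 60% receipt assumed for each item, either runs from 60% to 100% and both from 20% to 60%. The gap is zero if the items always go together and 48 points if they are received independently. These rates are assumptions. A reader might take the independent case (84% against 36%) as evidence that receipt will look successful while the benchmark fails; the protocol gives no item rates or overlap to support that.

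This is more than detail left to the analysis plan, because following the stated rule produces a number that does not measure the stated benchmark. The differing understanding denominators are a separate and smaller inconsistency in a secondary endpoint and add no weight to the point on receipt.

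**What to change.** - In sections 4, 9.3.2 and 9.7.2.4, define the primary receipt percentage as receipt of both brochure and card, to match the benchmark in sections 4 and 8.2.
- Report receipt of the brochure, of the card, of both and of neither, each with an exact 95% confidence interval, separately for patients and caregivers. This also serves a reader who takes the benchmark as a majority for each item.
- Keep receipt of at least one item as a supportive figure only.
- Use one denominator for understanding in sections 4, 9.3.2 and 9.7.2.4: those who read at least one of the materials. Do not split it by which item was read, because section 9.9 says that questions of this kind refer to the materials in general.

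The cost is wording in three sections and a headline receipt figure that may be lower. No new data are needed provided that the questionnaire records receipt of each item; this should be checked against the questionnaire before the text is changed.

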9.7.2.5 Sensitivity Analysis

9.7.2.5.1 Subgroup Analysis

The results will be presented overall and by country, educational level, and whether the materials were read or not.

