9.2.3 Subject Eligibility

9.2.3.1 Inclusion Criteria

- Patient/caregiver **completing questionnaire** is 18 years of age or older.
- Patient and/or caregiver of a patient with Ph- R/R B-precursor ALL who has received Blincyto **as an outpatient**.
- Patient/caregiver **completing questionnaire** can read and understand the native language of the country in which the study is being conducted.

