9.3 Variables

The questionnaire will contain multiple-choice questions with no free text fields.

The patient/caregiver questionnaire will be structured as follows:

- A. Acceptance to participate (Informed consent: date and signature **as required**)
- B. Screening: eligibility, demographics
- C. Main questionnaire domains

Section B (Screening) will collect socio-demographic characteristics (age, gender, educational status) about patients/caregivers. The questionnaire will be designed to take a maximum of 10-15 minutes to complete.

The questionnaire will assess the following key concepts related to the patient/caregiver card and brochure:

- Receipt of the patient/caregiver brochure and card.
- Knowledge about key information in the patient/caregiver brochure.
- Behaviours outlined in the patient/caregiver brochure and card.
- Usage of the patient/caregiver brochure and card i.e. whether the patient card is filled in with the required information, whether the patient card is shown to healthcare providers while on treatment with Blincyto, whether patients/caregivers read and refer to the educational materials and reasons for not reading them.
- Understanding of the patient/caregiver brochure and card.

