Only patients/caregivers able to understand and complete the informed consent and questionnaire will be included in the survey. Efforts will be made to write the questions in such a way that they can be readily understood by patients/caregivers with different educational levels so that ineligibility and inaccurate or missing responses for this reason are kept to a minimum. Non-response of items should be minimized due to the rigorous process of questionnaire development, validation and testing.

Patients/caregivers' responses may be biased if they are allowed to refer to the aRMM educational brochure and patient card. As a result, this would be minimized by explaining that responses should be based on assessing what they currently know and that they should not refer to the materials. At the time of completing the questionnaire, in the hospital clinic setting keeping materials out of reach should be readily feasible.

Self-reporting of actions and behavior may be biased towards positive values. The development of a questionnaire carefully pre-tested before actual study starts aims to minimize such a bias.

Recall bias is an inherent limitation of questions asking about the past. However, in this situation where **cycles** of therapy **are** administered over a short period of time (28 days **each**), this should be minimal.

The conduct of the survey may cause centres to provide more information to patients and caregivers. This 'Hawthorne' effect will be minimized by training sites to provide limited information about the survey in communications with the patients/caregivers.

The size of the study populations will allow an acceptable level of precision (considering the rarity of the disease) for each strata (patients and caregivers) for the study primary endpoints. Subgroup analyses will be exploratory and limited due to the small number of patients.

10. Protection of Human Subjects

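### The read versus not-read subgroup is not limited to recipients, so mean knowledge and behaviour scores among non-readers mix people who never received the materials with people who received but did not read them (minor)

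*Protocol*

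**What the plan says.** Section 9.7.2.5.1 of the protocol lists the subgroup factors in one sentence: "The results will be presented overall and by country, educational level, and whether the materials were read or not". The Data Analysis part of the abstract (section 4) names the same factor as an example: "certain subgroups, such as those who read the material vs. those who did not". Both give two levels, and neither restricts the factor to recipients of the materials.

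Four other places bear on the point.

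- Eligibility (9.2.3.1) rests on outpatient treatment, not on having been given the materials: "Patient and/or caregiver of a patient with Ph- R/R B-precursor ALL who has received Blincyto" as an outpatient.
- Receipt is a primary endpoint (9.7.2.4) and "will be assessed through the percentage of patients and caregivers who received the brochure and/or card".
- Reading is collected under usage (9.3): "whether patients/caregivers read and refer to the educational materials and reasons for not reading them". Section 9.3.2 adds: "Among patients and caregivers who have not read the materials, a categorical variable will describe the reasons for not reading them". That group is not limited to recipients either.
- Section 9.9 sets the status of these tables: "Subgroup analyses will be exploratory and limited due to the small number of patients".

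**The concern.** Receipt is an outcome of the survey, so some respondents may not have received the materials. Such a person has ordinarily not read them and, on the plain wording, is counted as not read. That column would then hold two kinds of respondent: those the programme did not reach, and those it reached who did not read what they were given.

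The distinction matters for how the survey is used. Section 8 asks separately whether the information reached its audience and whether the materials are used as intended. Section 9.1 justifies the timing of the survey by the chance to correct the programme early. Section 8.2 says that the results will be read in the context of the wider study, and that external information too "will be considered to determine what action, if any, should be taken". Non-receipt points to delivery by centres. Receipt without reading points to the material itself or to engagement with it. If knowledge is low among non-readers, a reader of the table would want to know which group it is low in.

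**Working it through.** The protocol gives no figure for this point, and the sample size and precision values are redacted, so there is nothing to reproduce. The check is a logic check with assumed rates.

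**Notation.** R is the proportion who received the materials. q is the proportion of recipients who read them. For the arithmetic, all readers are taken to be recipients. Then:

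- proportion not read = 1 − Rq
- non-recipient share of the not-read group, w = (1 − R)/(1 − Rq)
- proportion with receipt within the not-read group = R(1 − q)/(1 − Rq) = 1 − w

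**Step 1. The not-read percentage alone does not fix the mix.** Each assumed pair below gives 40% not read.

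| R | q | Not read, 1 − Rq | w | Receipt within not-read |
|---|---|---|---|---|
| 0.60 | 1.00 | 0.40 | 0.40/0.40 = 100% | 0% |
| 0.75 | 0.80 | 0.40 | 0.25/0.40 = 62.5% | 37.5% |
| 0.80 | 0.75 | 0.40 | 0.20/0.40 = 50% | 50% |
| 1.00 | 0.60 | 0.40 | 0/0.40 = 0% | 100% |

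The last column shows that the counts are recoverable: once receipt is tabulated within the not-read group, w is known.

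**Step 2. Range of w.** Table 2 runs over 60 to 90%. That is a grid for confidence-interval precision, not a forecast of receipt, and it is used here only as a span. Reading among recipients is assumed to lie between 50 and 95%. Since w falls as R rises and rises with q, the extremes are at two corners:

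- lowest, R = 0.90, q = 0.50: 0.10/(1 − 0.45) = 0.10/0.55 = 18%
- highest, R = 0.60, q = 0.95: 0.40/(1 − 0.57) = 0.40/0.43 = 93%

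Non-recipients may be a small minority of the not-read group or nearly all of it.

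**Step 3. Effect on a mean score.** Let m0 be mean knowledge among non-recipients and m1 the mean among recipients who did not read. The not-read mean is w·m0 + (1 − w)·m1. With assumed values m0 = 0.40 and m1 = 0.60:

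- w = 100%: 0.40
- w = 50%: 0.5 × 0.40 + 0.5 × 0.60 = 0.50
- w = 0%: 0.60

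The column mean moves across the whole interval with the mix, although neither group's knowledge has changed.

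**Step 4. Knowing w does not separate the means.** Take w = 50% and an observed not-read mean of 0.50. Then m0 + m1 = 1.00. The pairs (0.40, 0.60), (0.50, 0.50) and (0.60, 0.40) all fit. This is one equation in two unknowns, so the receipt percentages cannot supply the missing contrast. Scores cross-classified by receipt and reading are needed. The same holds for behaviour.

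**The case against.** The strongest reply is that the study measures the two failures separately. Receipt is a primary endpoint. Reading is a usage item. Reasons for not reading are tabulated. The results shown by reading status include receipt, so receipt within the not-read group comes out of the plan as written. All of this stands. A reader might infer that the survey cannot tell a distribution failure from a reading failure, or that it throws receipt data away. The documents support neither: both variables are collected and the number in each group can be read off. What the reply does not reach is knowledge and behaviour within each group (step 4). A not-received option among the reasons, if there is one, would add counts but not scores.

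A second reply is that coding a subgroup factor is work for the SAP (section 9.7), which is not shown, and that section 9.7.2.5.1 never says where non-recipients go. This has weight. Pooling follows from the plain wording, not from an explicit statement, and the questionnaire, a stand-alone document, may put the reading item to recipients only. The point survives because the protocol itself names the two levels in two places, and a SAP that follows it literally would produce the pooled column.

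Third, these tables are descriptive and exploratory, about 10 centres are planned, and patients and caregivers are analysed separately. A further split may leave very sparse cells. That is a real cost and limits the severity.

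Fourth, three levels are not perfectly clean. A caregiver may have read the patient's copy without receiving one, and receipt counts either item, so some people will have had only the card or only the brochure. The fix needs a rule for these cases.

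**Conclusion.** The point holds in a narrow form. Read as written, section 9.7.2.5.1 and the abstract place non-recipients with recipients who did not read, and mean knowledge and behaviour in that column cannot be attributed to either group. The size of each failure remains visible from the receipt endpoint and from receipt within the not-read group.

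The conclusion assumes that the reading item is not put to recipients only and that the SAP does not refine the factor. The 18% to 93% range rests on assumed receipt and reading rates and on readers being a subset of recipients. A reader might also infer that the contrast with readers is mainly a contrast with non-recipients. That holds for some assumed rates and fails for others, so it should not be asserted.

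No sample size, test or error rate is affected. Severity is minor.

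**What to change.** In section 9.7.2.5.1, and in the matching phrase of the abstract, define the factor for the knowledge and behaviour results as three levels: not received; received but not read; read. Count anyone who read a shared copy as read, and state how people who received only one of the two items are classified. Alternatively, limit read versus not read to recipients and show non-recipients in a separate column.

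Receipt and reading are already collected, so no new data are needed. The cost is two short text edits, one more column, and smaller cells in tables that are already exploratory. Showing the number of respondents in each cell would let readers judge how much weight a mean can bear.
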